- Perform a full physical examination including height (cm) and weight (kg).
- Record pertinent medical history including tobacco, illegal substance and alcohol history and current use.
- Administer the Physician's Global Assessment (PGA) and the Psoriasis Area Severity Index (PASI).
- Calculate the plaque BSA of the area(s) to be treated.

Treatment Period

Visit 1 Baseline (Day 1 [± 2 Days])

Eligible subjects will have the following procedures completed at Visit 1 (Baseline). It is possible for the patient to be screened and complete the Visit 1 (Baseline) procedures on the same day.

- Review inclusion and exclusion criteria to ensure the patient qualifies for the study.
- If this visit is NOT combined with the screening visit:
 - Perform an abbreviated physical examination including weight (kg),
 - Update concomitant medications including all prescription drugs, non-prescription drugs and nutritional supplements
 - Review and update the patient's pertinent medical history.

- Complete the PGA (only treatment area(s) are to be evaluated), PASI and tolerability assessment (only treatment area(s) are to be evaluated) including calculating the BSA of the affected area (only treatment area(s) are to be evaluated).
- If patient is a female of childbearing potential, collect a urine sample and perform a β -human chorionic gonadotropin pregnancy test.
- Instruct the patient on proper washing of the target treatment area(s) (using only study-approved cleanser) and application of SAN021 study medication on the treatment areas during the treatment period.
- Photograph the treatment area(s).
- Replace the cap with the dropper cap and weigh full bottle of SAN021 study medication and record weight prior to on site first dose.
- With the dropper cap on, weigh bottle of SAN021 study medication post on site dose and dispense to subject.
- Instruct the subject to return in one week for the next study visit with the study drug

Visit 2 (Day 7 [± 2 Days]), Visit 3 (Day 14 [± 2 Days]), Visit 4 (Day 28 [± 2 Days])

All study visits have a ± 2 -day visit window.

- Query for adverse events.
- Update concomitant medications including all prescription drugs, nonprescription drugs, and nutritional supplements.
- Query for treatment regimen compliance.
- Weigh and record the weight of the study medication and re-dispense.

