## 2.0 STUDY DESIGN

### 2.1 Overview of Study Design

This trial will be a double blind, multi-center, randomized, placebo controlled study to evaluate the safety, tolerability, and efficacy of SAN021 when administered topically for up to 42 days to adults between the ages of 18 to 65 years inclusive who have a clinical diagnosis of mild-to-moderate plaque psoriasis. Subjects will enter the Screening Period once the informed consent and photographic consent process has been completed. Subjects with mild-to-moderate plaque psoriasis, as defined by a PASI score between 2 and 12, that, in the opinion of the investigator, is appropriate for topical treatment, covers a minimum of 1.0% and a maximum of 10.0% body surface area in the permitted treatment areas, and who meet all of the inclusion and none of the exclusion criteria will be enrolled.

Once subject eligibility is confirmed and the screening procedures completed, all enrolled subjects will start the Treatment Period of the study. All enrolled subjects will receive either 10% SAN021

or placebo serum (randomized in a 2:1 ratio) with the first dose applied at the Day 1 Study Visit. Subjects will be instructed on how to apply the study medication twice daily for 42 days. Subjects will return to the clinic for study-related assessments on Study Days 7, 14, 28 and a final visit on Day 42. On Study Day 49, subjects will receive a follow-up phone call and be queried for condition status since going off study.

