## 5.2 Study Product and Visit Compliance

All analyses in this section will be performed using the Safety Population. Study visit attendance will be summarized by study arm for each follow-up visit. The count and percent of subjects who attended their visit will be calculated.

Study product compliance parameters will be summarized using descriptive statistics for each study arm. These parameters include the following:

- Number of applications missed (quantitative assessment)
- Total weight of product used (quantitative assessment)
- Average weight per application of product (quantitative assessment)
- The number and percentage of subjects who received fewer than 60% of prescribed applications (and considered non-compliant with the treatment) at each visit, and over all follow-up visits.

Compliance will be based on the baseline body surface area (bsa) of the treated area times 0.25 ( $W=bsa \times 0.25$ ). The number of applications per study day is two, and will be assumed to be one on each visit day, except baseline, which will be assigned two applications. The number of applications (X) for an interval will then be:

- from baseline to a follow-up visit:  $X = (\text{current visit date} - \text{baseline date}) \times 2 + 1$
- from a follow-up visit to a subsequent follow-up visit:  
$$X = (\text{current visit date} - \text{previous visit date}) \times 2;$$

and therefore, the expected weight of drug applied (EW) will be calculated as:

$$EW=X(W)$$

The actual amount of drug applied in an interval (AW) will be the difference between the bottle weights at the relevant visits:

$$AW = \text{weight of bottle at current visit} - \text{weight of bottle at previous visit}$$

The actual compliance will be calculated as the percentage (C) of what was used versus what was expected to be used:

$$C = (AW/EW) \times 100$$

This value may be greater than 100%. However, if the value is less than 60%, then the subject will be considered non-compliant for that study treatment interval.

Using these same calculations, compliance over all follow-up visits will be calculated using available data from the medication dispensation log. Weight of drug used from a bottle will be the difference of the last medication weight reported and the weight of the bottle at dispensation. If multiple bottles are used, cumulative product weight will be calculated.

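### SAP 5.2 counts the on-site first dose in expected use, but overall use appears to be weighed from after that dose, and the first interval's starting weight is undefined

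*SAP*

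**What the plan says.** - **Expected use.** In SAP 5.2 the number of applications "will be assumed to be one on each visit day, except baseline, which will be assigned two applications". The count "from baseline to a follow-up visit" is X = (days between the two dates × 2) + 1, and between two follow-up visits it is days × 2. The expected weight is EW = X × W, with W equal to baseline BSA × 0.25.
- **First dose.** SAP 2.1 starts treatment "with the first dose applied at the Day 1 Study Visit". One of the two baseline applications is therefore the on-site dose.
- **Actual use, by interval.** SAP 5.2 takes AW from the bottle weights at the current and previous visits. It does not say which baseline weighing counts as the previous visit's weight in the first interval.
- **Actual use, overall.** SAP 5.2 uses "the difference of the last medication weight reported and the weight of the bottle at dispensation", cumulated if there is more than one bottle.
- **Weighings at baseline.** The protocol's Visit 1 procedures have site staff "weigh full bottle of SAN021 study medication and record weight prior to on site first dose" and then, with the dropper cap on, "weigh bottle of SAN021 study medication post on site dose and dispense to subject".
- **Use of the result.** Compliance C = 100 × AW/EW. A value below 60% makes an interval non-compliant (SAP 5.2). Average usage below 60% over the whole of participation is a major violation that removes a subject from the per-protocol set (SAP 3.3).

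**The concern.** The numerator and denominator of overall compliance do not cover the same applications. X includes the on-site dose, yet the protocol links dispensing to the weighing done after that dose, so its grams are missing from AW. Every subject has a first bottle, and under this reading the error has one direction and does not average out.

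The first by-visit interval has a different problem: two baseline weights are available and the SAP names neither. Two programmers following SAP 5.2 could produce different Day 7 results. If the interval starts from the pre-dose weight while overall use starts at dispensation, the interval weights will not add up to the total.

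At stake are the product compliance summary (Table 14.2.1.2) and the compliance criterion for the per-protocol set. Table 14.2.1.2 is the only planned table of the amount of product used, in a trial whose primary objective is safety. Total weight used is affected in the same way, and so is average weight per application if X is its divisor.

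**Working it through.** **Inputs.** The application rule, X, W, EW, AW, C and the 60% line come from SAP 5.2. Visit days 7, 14, 28 and 42, each ±2 days, come from SAP Table 2.1. The two baseline weighings come from the protocol's Visit 1 procedures. The documents do not give the weight of the on-site dose; I write it as r × W, take r = 1 and show r = 0.5 to 2. AW is written as current minus previous weight, which is negative for a bottle being used up. I take it with the sign reversed; that is a separate matter.

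**1. Reproduce X.** With the baseline visit as Day 1, a visit on Day d gives X = 2(d − 1) + 1. A direct count gives 2 for baseline, 2 for each of the d − 2 days between, and 1 for the visit day: 2 + 2(d − 2) + 1 = 2d − 1, which is the same.
- Day 7: 2 × 6 + 1 = 13.
- Day 42: 2 × 41 + 1 = 83.
- The interval counts add up: 13 + 14 + 28 + 28 = 83.

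So X is internally consistent and includes the on-site dose.

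**2. Shift with a post-dose start.** AW loses rW while EW = XW is unchanged, so C falls by 100r/X points. The third column assumes r = 1 and exactly W used at each application.

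| Visit day | X | Nothing missed reads | Shift, r = 0.5 | r = 1 | r = 2 |
|---|---|---|---|---|---|
| 5 | 9 | 8/9 = 88.9% | 5.6 | 11.1 | 22.2 |
| 7 | 13 | 12/13 = 92.3% | 3.8 | 7.7 | 15.4 |
| 9 | 17 | 16/17 = 94.1% | 2.9 | 5.9 | 11.8 |
| 40 | 79 | 78/79 = 98.7% | 0.6 | 1.3 | 2.5 |
| 42 | 83 | 82/83 = 98.8% | 0.6 | 1.2 | 2.4 |
| 44 | 87 | 86/87 = 98.9% | 0.6 | 1.1 | 2.3 |

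The Day 40 to 44 rows are the overall figure under the dispensation rule. The Day 5 to 9 rows apply to the first interval only if the post-dose weight is also used there.

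**3. Later intervals.** Days 7–14, 14–28 and 28–42 use two follow-up weights and contain no on-site dose, so the shift is 0.

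**4. The 60% line, r = 1.** A subject changes class if the true C lies from 60 up to 60 + 100/X.
- Overall at Day 42: 60% to 61.2%. For example, 50/83 = 60.2% reads 49/83 = 59.0%.
- First interval at Day 7, post-dose start: 60% to 67.7%. For example, 8/13 = 61.5% reads 7/13 = 53.8%.

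**5. Adding up.** With a pre-dose start for the first interval and a dispensation start overall, a subject who misses nothing shows interval weights of 13W + 14W + 28W + 28W = 83W, but a total of 82W.

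**6. Would dropping the +1 do instead?** With the post-dose weight and X reduced by one, a subject who misses nothing reads 100%. Other subjects do not read the same as under a pre-dose start: 49/82 = 59.8% against 50/83 = 60.2% overall, and 7/12 = 58.3% against 8/13 = 61.5% at Day 7. Total weight used would still omit the on-site grams.

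**The case against.** **The post-dose reading is not certain.** The protocol uses the word record only for the pre-dose weighing. The dispensation rule in SAP 5.2 is stated per bottle and may simply mean each bottle's starting weight. The contents of the dispensation log cannot be seen. In addition, the SAP cites a protocol dated 08 August 2017 whose title includes double blind; the supplied synopsis has no such words in its title, so the weighing steps may differ between versions. This stands as a limit on confidence. It does not remove the ambiguity, since the supplied protocol ties dispensing to the post-dose weighing and the SAP does not say otherwise.

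**A reader might infer that every subject's compliance is understated throughout, and most of all at the first visit.** The documents do not support that. The dispensation wording governs only compliance over all follow-up visits. The first-interval weight is undefined rather than wrong, and a pre-dose start gives no error there. Later intervals do not move under either reading.

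**The consequence is small.** Per-protocol entry depends on usage over the whole of participation, where the shift is about 1.2 points at Day 42. Early discontinuers shift more because X is smaller, but those without a Day 42 observation already fail the per-protocol definition. SAP 8.0 makes the full analysis set primary and the per-protocol set supportive, SAP 2.2 plans no inferential analysis, and the same rule applies in both arms. All of this stands, and it limits the point to a clarification worth making.

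**Conclusion.** The point holds in limited form. On the natural reading of the two documents together, SAP 5.2 includes the on-site dose in expected use and leaves it out of overall actual use. For a subject reaching Day 42, overall compliance is about 1.2 points low (0.6 to 2.4), and only true values of about 60% to 61.2% would wrongly fail the per-protocol threshold. Total weight used omits the on-site grams. Average weight per application is also low if X is the divisor: 82W/83 = 0.988W for a subject who misses nothing.

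For the first interval the finding is an undefined starting weight. The choice decides between no error and a shift of 7.7 points at Day 7 (5.9 to 11.1 across the visit window, for an on-site dose of W).

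These sizes rest on the assumed weight of the on-site dose, on a corrected sign for AW, and on dispensation meaning the post-dose weighing. If it means the pre-dose weight, and the first interval starts there too, there is no error, only wording to tighten. No efficacy conclusion is threatened.

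**What to change.** In SAP 5.2, state that the starting weight of the first bottle is the recorded baseline weight before the on-site dose. Apply this to the first interval, overall compliance, total weight used and average weight per application, and leave X as it is. Later bottles keep their weight at dispensation, since no on-site dose precedes it.

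Do not instead keep the post-dose weight and remove the +1 from X. Step 6 of the working shows that this classifies some subjects differently and leaves the on-site grams out of total weight used.

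The cost is one sentence in the SAP and one line of code. No new data are needed, because the protocol already has the pre-dose weight recorded.

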## 6.0 EVALUATION OF BASELINE CHARACTERISTICS

Analyses in this section will be performed using the Safety Analysis Set by study arm and overall study arms.

## 6.1 Demographics

Demographic data will be summarized for the quantitative (or numerical) assessments (age, height (cm), and weight (kg)) and the qualitative (or categorical) assessments (gender, race, and ethnicity). If multiple races are reported for a single subject the count will be ascribed to the 'other' category. Percentages will be based on the number of non-missing responses. Results will be presented in by-subject listings.

## 6.2 Baseline Disease Characteristics

Disease characteristics at baseline will be summarized for quantitative assessments, percent of body surface area being treated and PASI, and the qualitative assessments, target treatment area and PGA score.

## 6.3 Medical History/Signs and Symptoms

Medical conditions reported in the medical history will be mapped to preferred term (PT) and system organ class (SOC) using the Medical Dictionary for Regulatory Activities (MedDRA 19.0). Results will be provided in a by-subject listing.

# 7.0 EVALUATION OF SAFETY PARAMETERS

All safety analyses will be performed using the Safety Analysis Set.

The safety parameters collected and monitored during this study include adverse events, treatment tolerability, and concomitant medications.

## 7.1 Adverse Events

An AE is any reaction, side effect, or other untoward event, regardless of relationship to study drug, that starts any time after the beginning of dosing. Non-serious AEs will be captured through the last treatment application, Day 42/exit, and serious AEs will be captured up through 28 days following the discontinuation of therapy.

All AEs reported will be considered to be treatment-emergent. Verbatim adverse events will be mapped to PT and SOC using MedDRA 19.0.

Tabular summaries of treatment-emergent adverse events (TEAEs) in terms of number of subjects will be presented by each study arm for the following:

- PT presented in order of descending incidence in the SAN021 group then alphabetically
- SOC and PT presented in order of descending incidence in SOC, then PT, in the SAN021 group, then alphabetically by SOC and PT
  - repeat presentation for subset of study-drug related events
- SOC, PT, and maximum severity grade (mild, moderate, severe) presented alphabetically by SOC and PT

Adverse events will be counted as treatment related if they are evaluated as possibly, probably, or definitely related to study treatment. Subjects will be counted once within each level of summarization within each study arm for the calculation of incidence.

A summary of count and percent of subjects with at least one event in the following categories will be tabulated: any TEAE, any mild TEAE, any moderate TEAE, any severe TEAE, any treatment-related TEAE, any serious TEAE, any TEAE that led to discontinuation of study drug, and any deaths.

A comprehensive listing of all AEs will be provided by subject, which will include the duration of each event. Duration will be calculated as the stop date of the event minus the start date, unless the event is determined ongoing at exit.

## 7.2 Treatment Tolerability

Treatment tolerability will be summarized at each visit by the number of subjects who experienced discomfort during or immediately following the study drug application (Yes, Discomfort).

Tolerability will be summarized over all follow-up visits by the number of subjects who reported discomfort at any visit during the study. In these analyses, all percentages will be based on the number of responses. Results will be provided in a by-subject listing.

## 7.3 Prior and Concomitant Medication/Therapy

All prior and concomitant medications will be coded with WHODrug (MAR2016) and results will be presented in a by-subject listing with prior or ongoing-at-baseline medication/therapy identified.

# 8.0 EVALUATION OF EFFICACY PARAMETERS

Analyses in this section will be based on the FAS and the PP analysis set. The primary set for efficacy analyses will be the FAS; supportive analyses will be based on the PP. All analyses will be performed by study arm with missing data imputed using the last observation carried forward.

## 8.1 Physician's Global Assessment

The PGA is a categorical assessment of psoriasis severity made according to the following scale:

Grade	Score	Description
Clear	0	No signs of psoriasis (post-inflammatory hyperpigmentation may be present)
Almost Clear	1	Intermediate between mild and clear
Mild	2	Slight scaling plaque elevation, scaling, and/or erythema
Moderate	3	Moderate plaque elevation, scaling, and/or erythema
Severe	4	Very marked plaque elevation, scaling, and/or erythema

The incidence of clear/almost clear grading (score of 0 or 1) will be summarized by visit. A summary over all follow-up visits will also be provided and is defined as the number and percentage of subjects achieving clear/almost clear at any time point during the 42 days of therapy.

Improvement in scores will also be calculated as change from baseline score (follow-up – baseline) by follow-up visit and over all follow-up visits; over all follow-up visits will be based on the best change from baseline (lowest value) at any time point during the 42 days of therapy. Improvement in score from baseline score will be assigned to the category of no improvement if either no change or a worsening score (positive change) occurs, or into one or both of the categories  $\geq 1$  grade improvement, and  $=2$  grade improvement (i.e., subjects with a 2 grade improvement will also be counted in the  $\geq 1$  grade improvement). Count and percent of subjects in each category will be provided.

The frequency distribution of scores by each visit will be provided, and the results will be presented in a by-subject listing.

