A. Physician's Global Assessment (PGA): The PGA will be based on a 5-point scale ranging from 0 (clear) to 4 (severe), and will be assessed, preferably by the same evaluator at each visit for the overall affected areas with plaque psoriasis which were treated with the study drug. The study exclusion areas and those areas not treated are not to be used in this assessment. The following scores will be used to describe the severity of overall plaque psoriasis of the treatable areas:

Grade	Score	Description
Clear	0	No signs of psoriasis (post-inflammatory hyperpigmentation may be present)
Almost Clear	1	Intermediate between mild and clear
Mild	2	Slight scaling plaque elevation, scaling, and/or erythema
Moderate	3	Moderate plaque elevation, scaling, and/or erythema
Severe	4	Very marked plaque elevation, scaling, and/or erythema

Data Analysis

Safety

The number and percentage of subjects reporting at least one occurrence of an AE for each unique System Organ Class and Preferred Term will also be tabulated by severity and by the relationship to trial drug. All AEs will be presented in a data listing.

Tolerability

Tolerability will be based on the number of subjects reporting discomfort during or immediately following application of SAN021, this will also be recorded as an AE.

Preliminary Efficacy

The efficacy will be assessed as follows:

- Percentage of subjects achieving at least a 1-grade improvement in PGA score
- Percentage of subjects achieving a 2-grade improvement in the PGA score
- Percentage of subjects who have a $\geq 25\%$ reduction in the Psoriasis Area and Severity Index (PASI) score at any point during the trial.
- Percentage of subjects who have a $\geq 50\%$ reduction in the Psoriasis Area Severity Index (PASI) score at any point during the trial.
- Number of subjects achieving a Physician's Global Assessment of "clear" or "almost clear" at any time point during the 42 days of therapy. The study restricted treatment areas are not to be included in this evaluation. (see #10 under Inclusion Criteria)

Planned Dates of Study

April 2017 to December 2017

Trial Contacts

Name	Affiliation / Address	Responsibility
Santalis Pharmaceuticals	[name]  [contact]  [contact]	Sponsor
[name], PhD	Santalis Pharmaceuticals [name]  [contact]  [contact] e-mail: [contact]	Sponsor Representative

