#### 1.1.2 Additional Objectives

Additional objectives are to evaluate tolerability and preliminary efficacy. Tolerability will be assessed based on the number of subjects reporting discomfort during or immediately following application of study drug in the treatment areas. Discomfort will also be recorded as an AE. Preliminary efficacy will be assessed based on the following summaries:

- Percentage of subjects who have a  $\geq 25\%$  reduction in the Psoriasis Area and Severity Index (PASI) score at any point during the 42 days of treatment.
- Percentage of subjects who have a  $\geq 50\%$  reduction in the PASI score at any point during the 42 days of treatment.
- Percentage of subjects with a PGA score of “clear” or “almost clear” at any time during the 42 days of treatment.
- Percentage of subjects achieving at least a 1-grade improvement in Physician’s Global Assessment (PGA) score.
- Percentage of subjects achieving a 2-grade improvement in PGA score.

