## 8.2 Psoriasis Area and Severity Index

The PASI is a continuous measure of psoriasis severity with scores that can range from 0 to 72 with higher scores indicating more severe conditions. For this study the population is required to have PASI scores between 2 and 12, inclusive, at baseline. Scores will be summarized by visit with n, mean, SD, median, minimum, and maximum. Change from baseline will be calculated (follow-up value – baseline value) and summarized by follow-up visit. Change values that are negative represent an improvement. Percent change from baseline ((follow-up value – baseline value)/baseline value) x 100 will also be summarized by follow-up visit.

Percent change from baseline will be assigned to one or more of the following categories:

Group	Percent Reduction Category	Percent change from baseline values
1	< 25% Reduction	$> -25.0$
2	$\geq 25\%$ Reduction	$\leq -25.0$
3	$\geq 50\%$ Reduction	$\leq -50.0$
4	$\geq 75\%$ Reduction	$\leq -75.0$

These groups are not mutually exclusive; results that fall into group 4 will also be counted in groups 2 and 3, likewise results that fall into group 3 but not group 4 will also be counted in group 2. The frequency distribution of subjects within each of these groups will be summarized by visit. A summary over all follow-up visits will include the number and percent of subjects achieving their best (lowest value/greatest reduction) percent change at any time point during the 42 days of therapy.

The results will be presented in a by-subject listing.

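### SAP 8.1 counts a 2-grade PGA improvement only when it is exactly 2 grades, so subjects who improve by 3 or 4 grades count as non-responders on that endpoint

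*SAP*

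**What the plan says.** The SAP lists five preliminary efficacy summaries in section 1.1.2. One of them is "Percentage of subjects achieving a 2-grade improvement in PGA score". The companion 1-grade endpoint carries the qualifier at least, and the 2-grade endpoint does not. The protocol synopsis draws the same contrast under Preliminary Efficacy Evaluation and again under Data Analysis.

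SAP section 8.1 turns these into three categories of change from baseline:

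- No improvement: a subject is "assigned to the category of no improvement if either no change or a worsening score (positive change) occurs".
- Improvement of one grade or more, written with ≥.
- Improvement of two grades, written with = and followed by the explanation: "2$ grade improvement (i.e., subjects with a 2 grade improvement will also be counted in the" one-grade category. (The dollar sign is residue of text extraction. The equals sign stands just before the quoted words.)

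On the summary across visits, the SAP states: "over all follow-up visits will be based on the best change from baseline (lowest value) at any time point".

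On the scale itself, the protocol states: "The PGA will be based on a 5-point scale ranging from 0 (clear) to 4 (severe"). SAP section 4.1.2 sets the default denominator as all subjects of the arm in the analysis population.

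SAP section 8.2 handles the PASI reduction groups differently. There, "results that fall into group 4 will also be counted in groups 2 and 3".

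**The concern.** A responder endpoint on an ordered scale should be a threshold: anyone who does better than the threshold has also met it. As written, the 2-grade category has no open upper end. The explanatory clause in section 8.1 only places 2-grade improvers in the 1-grade category. It does not bring 3- or 4-grade improvers into the 2-grade category. A programmer following the text would code change = −2.

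The rule therefore leaves out the best responders. If SAN021 works, one would expect more of them in the SAN021 arm, so the rule would understate that arm's rate and its difference from placebo. The by-visit rate can also fall as subjects get better, because moving from −2 to −3 leaves the category.

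**Working it through.** The plan gives no figure for this endpoint (no expected rate, power or alpha), so there is nothing to reproduce. The check applies the rule to every possible case.

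**Inputs**

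- PGA scale 0 to 4 (protocol synopsis; SAP 8.1).
- Change = follow-up − baseline, so improvement is negative (SAP 8.1).
- Categories: change ≥ 0 is no improvement; change ≤ −1 is the 1-grade category; change = −2 is the 2-grade category (SAP 8.1).
- Over all visits: the lowest change (SAP 8.1).
- Entry severity is set on PASI and body surface area, "as defined by a PASI score between 2 and 12", with no PGA limit (SAP 2.1).
- 72 subjects planned, at least 60 completing, allocated 2:1 (SAP 2.1 and 2.2).

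**Step 1. All transitions of two grades or more**

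| Baseline → follow-up | Change | Counted in ≥1 grade | Counted in =2 (as written) | Counted if ≥2 |
|---|---|---|---|---|
| 2 → 0 | −2 | yes | yes | yes |
| 3 → 1 | −2 | yes | yes | yes |
| 4 → 2 | −2 | yes | yes | yes |
| 3 → 0 | −3 | yes | **no** | yes |
| 4 → 1 | −3 | yes | **no** | yes |
| 4 → 0 | −4 | yes | **no** | yes |

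Three of the six possible transitions are missed. This counts cells, not subjects. Two of the three need a severe (4) baseline, which is not barred but should be uncommon in a mild-to-moderate population. From baselines 2 and 3 only, one of three qualifying transitions (3 → 0) is missed, and that is the realistic case.

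**Step 2. Best-change rule**

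Take baseline 3 and scores of 2, 1, 1, 0 at the four follow-up visits. The changes are −1, −2, −2, −3. The subject counts as =2 at the second and third visits. The best change is −3, so the subject is not counted over all visits.

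**Step 3. Size per subject**

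A missed subject stays in the denominator, so each one costs 1/n:

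- 72 analysed (48 and 24): 1/48 = 2.1 points on SAN021; 1/24 = 4.2 points on placebo.
- 60 analysed (40 and 20): 1/40 = 2.5 points; 1/20 = 5.0 points.

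**Step 4. Range under assumed counts**

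The documents give no PGA response rates, so these counts are assumptions. In an arm of 48 with 10 exact 2-grade improvers:

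| Further 3- or 4-grade improvers | Rate as written | Rate with ≥2 |
|---|---|---|
| 0 | 10/48 = 20.8% | 10/48 = 20.8% |
| 2 | 20.8% | 12/48 = 25.0% |
| 5 | 20.8% | 15/48 = 31.25% |
| 10 | 20.8% | 20/48 = 41.7% |

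The order of the arms can also reverse. Suppose SAN021 has 8 exact 2-grade and 8 three-grade improvers of 48, and placebo has 5 exact 2-grade improvers of 24 and none above. As written, the table shows 8/48 = 16.7% against 5/24 = 20.8%. With ≥2 it shows 16/48 = 33.3% against 20.8%.

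**The case against.** The strongest reply is that little depends on this row. The primary objective is safety, this is one of five preliminary summaries, and SAP 2.2 rules out inferential analysis, so no test, alpha or power is affected. The missed subjects are not classed as unimproved. They count in the 1-grade category and, because each missed transition ends at 0 or 1, in clear/almost clear as well. The by-subject PGA listing (16.2.6.4) allows a ≥2 count to be rebuilt. The likely error works against SAN021, so it would not inflate a claim of benefit. The realistic loss is confined to complete clearance from moderate disease within 42 days, which may be rare.

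All of this is correct, and it limits the size of the effect. It does not make the category right. In a purely descriptive plan the printed percentages are the result. The by-visit score distribution gives marginal counts, not within-subject change, so in general a reader of the tables alone cannot recover the correct rate.

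The equals sign could also be a drafting slip or an extraction error. Extraction is unlikely, because ≥ survives in the same sentence and the prose in SAP 1.1.2 and the protocol also omits the qualifier for two grades. A drafting slip is plausible, and it needs the same correction.

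**Conclusion.** The concern holds. Read as written, SAP 8.1 leaves every 3- or 4-grade improver out of the named 2-grade PGA endpoint, by visit and over all visits, and further improvement can remove a subject who had already qualified. No other text in the protocol or SAP supplies the missing qualifier. The failure is confined to that endpoint.

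The cost is 2.1 points per affected SAN021 subject and 4.2 per placebo subject, assuming all 72 enter the Full Analysis Set at 2:1. The total effect depends on how many subjects improve by more than two grades, which the documents do not allow one to estimate. It is zero if none do. The expected direction, against SAN021, assumes that the product works and that large improvements are more common on it.

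**What to change.** In SAP 8.1, replace the =2 category with ≥2 grade improvement (change from baseline ≤ −2), nested within ≥1 grade in the way the PASI groups are nested. Apply it by visit and over all visits, and make the shell for Table 14.2.2.2.X match (the shells are in a separate document that was not available to check).

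It is also sensible to align the endpoint wording in SAP 1.1.2 and in the two protocol synopsis lists, so that both PGA improvement endpoints read as thresholds. If exactly two grades is really intended, the SAP should say so and give the reason.

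The cost is one symbol and one programming condition, with no new data. It should be settled before unmasking, so that the definition is not chosen with results in view.
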